8.3. Study Drug Compliance

Not applicable for the current study. Drug compliance during study duration will not be assessed.

8.4. Adverse Events

Adverse events will be collected and recorded from the time a patient signs the informed consent to the end of follow-up period.

All adverse events will be coded using the Medical Dictionary for Regulatory Activities (MedDRA version 26.0 or later). Unless otherwise specified, adverse events will be summarized by SOC and preferred term, with preferred terms within SOCs presented in descending order of patient incidence. Multiple records with the same PT or SOC category and adverse event onset date for the same patient, or with overlapping or consecutive dates, are counted only once for the adverse event with the highest severity and seriousness.

Adverse events summaries will be presented for Period 1 separately and for the integrated study periods separately. Adverse events that started in Period 1 and ended in Period 2 will be reported only in Period 1, and will be presented only once in the integrated summary table.

Summaries will include treatment-emergent adverse events that are defined as adverse events that occurred at or after the first IMP injection was administered through the end of the treatment (including the assessment collected in the End-of-Treatment/ Early Termination visit).

Additional summaries will be presented for the follow-up period (after the End of Treatment/Early Termination visit and until the end of the study).

Summaries will be presented for all adverse events (overall and by severity), including adverse events defined by the investigator as related or with missing relationship to IMP treatment and/or device (overall and by severity), serious adverse events, serious adverse device events and adverse events and adverse device events causing withdrawal from the study and withdrawal from the treatment. All summaries will be presented by treatment group and overall (total), using exposure categories.

Protocol defined adverse event of special interest (PDAESI) (section 8.1.7 of the study protocol) will also be summarized and presented by treatment group and by visit..

The summary tables for adverse events will be presented by the treatment group to which the patient were assigned according to the safety analysis set. A separate summary tables will be presented, excluding the patients with at least one dose adjustment. Additional analysis may be initiated if the results of those summaries will judged by the study team to be significantly different.

Patient listings of serious adverse events, adverse events leading to treatment discontinuation and study withdrawal, and adverse events leading to death will be presented. Patient's dose at the time of the Adverse Event onset will be included in all listings.

In case of the missing dates and severity, the imputation will be performed as described in Section 4.3.

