8.1. Adverse Events

8.1.1. Definition of an Adverse Event

An adverse event is any untoward medical occurrence in a patient or clinical investigation subject administered a pharmaceutical product and which does not necessarily have to have a causal relationship with this treatment.

An adverse event can, therefore, be any unfavorable and unintended physical sign, symptom, or laboratory parameter that develops or worsens in severity during the course of this study, or significant worsening of the disease under study, or of any concurrent disease, whether or not considered related to the IMP.

Accordingly, an adverse event can include any of the following:

- a new condition or the worsening of a pre-existing condition
- intercurrent illnesses
- physical injuries and the mechanism that caused the injury
- events possibly related to concomitant medication
- drug/drug interactions
- events occurring during diagnostic procedures or during any washout phase of this study
- laboratory or diagnostic test abnormalities

(Note: Abnormal laboratory or diagnostic test results at the screening visit that preclude a patient from entering the study or receiving study treatment are not considered adverse events.)

In Period 2, worsening of the schizophrenia will be assessed using PANSS, CGI-I, and CGI-S and should be recorded as an adverse event per investigator judgment.

A relapse event will be classified as an adverse event if specifically assessed as such by the investigator.

An adverse device effect is an adverse event related to the use of a medical device or a combination product. This includes adverse events resulting from insufficient or inadequate instructions for use, deployment, implantation, installation, operation, or any malfunction of the

medical device, including any event resulting from user error or from intentional misuse of the medical device. This definition includes events related to the procedures involved. For users or other persons, this definition is restricted to events related to medical devices.

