3.3. Safety Analysis Set

The safety analysis set for Period 1 will include all randomized patients who received at least 1 dose of TV-44749 or placebo. The safety analysis set for Period 2 will include all randomized patients to Period 2 who received at least 1 dose of TV-44749. For the integrated study periods summary tables (see Section [8](#)) the safety analysis set will include all patients in the safety analysis set of period 1 that received 1 of the 3 TV-44749 treatments groups, or all patients that meet the definition of the safety analysis set of Period 2.

In each of the safety analysis sets, treatment will be assigned based on the initial treatment patients actually received in the corresponding period, regardless of the treatment to which they were randomized, and regardless of dose adjustments, unless otherwise specified. For the integrated periods summary tables, patients randomized in Period 1 to 1 of the 3 TV-44749 groups will be counted according to the initial dose they actually received in Period 1. Patients that were randomized to Placebo in Period 1 will be counted according to the initial dose of TV-44749 they actually received after the re-randomization of those patients to the 1 of the 3 TV-44749 treatment groups in Period 2, regardless of dose adjustment that may occur during Period 2.

In cases of dosing error, a decision of what is the treatment assignment for these patients will be made in a blinded manner prior to unblinding of Period 1, as applicable. The decision will be made during the statistical data review meeting and will be documented in the statistical data review document.

For IDMC monitoring during the study, the safety analysis set will use the treatment based on the randomization assignment in the opening of each period.

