8. SAFETY ANALYSIS

8.1. General

Safety analyses will follow the safety estimand approach using the safety analysis sets.

Safety will be assessed by qualified study personnel by evaluating reported adverse events (including serious adverse events, extrapyramidal symptoms, injection pain, injection site findings and Injection Site Reactions [ISRs]), vital signs (blood pressure, pulse and orthostatic changes, and temperature), body weight and BMI, laboratory tests, ECG, concomitant medication use, time to all-cause discontinuation, all-cause discontinuation rates and discontinuation rates due to adverse events (tolerability), time to all discontinuation by reason, and safety rating scales (including Abnormal Involuntary Movement Scale [AIMS], Barnes Akathisia Rating Scale [BARS], Simpson-Angus Scale [SAS], C-SSRS, and CDSS).

Safety assessments and time points are provided in Table 1 (for Period 1) and Table 2 (for Period 2) of the study protocol.

The safety analysis will be performed separately for Period 1 and for the integrated study periods.

The safety analysis for Period 1 will be performed by treatment group and overall (total).

The safety analysis for the integrated study periods that will be presented in the CSR and in the IDMC closed reviews, will be performed by treatment group. Specifically, for IDMC closed reviews, patients rolling over from Placebo group will be distinguished from patients who continued their active treatment assignment from Period 1. Data from Period 1 for placebo patients will not be included in the integrated summaries.

For the open sessions of the IDMC reviews, data from Period 1 and from Period 2 will be presented separately. Summary tables will be generated for each period and will only be presented as a single total column.

For the following safety variables: Adverse events, Clinical laboratory results, ECG, weight and BMI and Vital signs, a separate safety summary will be presented for the 'While on Treatment' period, defined as the period between the first IMP administration visit until and including the End of Treatment visit (including the Early Termination visit if conducted during this period). In addition a separate safety summary table and listing will be presented for the Follow-Up period, defined as the period after the End of Treatment/Early Termination visit until the end of the study.

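### SAP 8.1 and 8.4 conflict on adverse events that begin on placebo and continue onto TV-44749, and on-drug worsening can land in the placebo column

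*SAP*

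**What the plan says.** Placebo patients who complete Period 1 and qualify for Period 2 are re-randomized 1:1:1 to the three TV-44749 doses at Visit 11 (SAP 2.1).

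SAP 8.4 sets three rules for adverse events:

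- **Period.** "Adverse events that started in Period 1 and ended in Period 2 will be reported only in Period 1". The sentence then continues: "and will be presented only once in the integrated summary table".
- **Merging.** A patient's records in the same term category with the same onset date, "or with overlapping or consecutive dates, are counted only once for the adverse event with the highest severity and seriousness".
- **Treatment emergence.** The summaries cover "adverse events that occurred at or after the first IMP injection was administered through the end of the treatment". Protocol 6.1 defines IMP to include the matching placebo.

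Two further SAP rules govern the integrated tables. SAP 8.1 says: "Data from Period 1 for placebo patients will not be included in the integrated summaries". SAP 3.3 fixes the column: "Patients that were randomized to Placebo in Period 1 will be counted according to the initial dose of TV-44749 they actually received".

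The protocol's list of what can be an adverse event includes "a new condition or the worsening of a pre-existing condition" (Protocol 8.1.1). Each event carries one severity grade (Protocol 8.1.3) and an onset and end date (Protocol 8.1.2).

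**The concern.** The period rule looks only at onset, but for former-placebo patients the treatment changes in the middle of the event. Nothing in SAP 8.4 limits the grade shown in a Period 1 table to what was reached before the Visit 11 injection. Nothing says how worsening after the first TV-44749 dose is to be counted. SAP 4.2 resets the baseline of measured values for these patients at Period 2, but adverse events have no matching rule.

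Safety and tolerability is a secondary objective. Period 1 supplies the only placebo-controlled safety comparison, and the integrated tables supply the long-term exposure data. No other table by treatment group catches a misplaced event, because SAP 4.1 and 8.1 plan the CSR safety tables as Period 1 and integrated only. The events at issue are severe or serious ones, where counts are low and a few patients are visible.

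**Working it through.** The documents state no figure on this point, so there is none to reproduce. The check is a trace of the rules, followed by a rough sizing.

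**Rule trace.** Take a former-placebo patient whose first TV-44749 injection is on day 57 (Visit 11). The event starts mild on day 40 and is severe or serious from day 70.

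- **A. One record, days 40 to 90.** Onset is in Period 1, so the event goes to the Period 1 placebo column at the higher grade.
- **B. Two consecutive records, mild days 40 to 69 and severe days 70 to 90.** If records are merged before the period is assigned, the result is one severe Period 1 event on placebo. If the period is assigned record by record, the severe record falls in Period 2 on TV-44749. The SAP does not give the order.
- **C. Two records with a gap, mild days 40 to 50 and severe days 70 to 90.** The severe record falls in Period 2 on TV-44749, which is correct.

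Misattribution therefore follows in A, in B under one order of the rules, and not in C. The period rule is also worded for events that ended in Period 2, so it is silent on events that never resolve.

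**Integrated tables.** SAP 8.1 and the second half of the 8.4 sentence give different results for an event with placebo onset:

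| Event with placebo onset | If SAP 8.1 governs | If the 8.4 clause governs |
|---|---|---|
| Unchanged after crossover | Not in a TV-44749 column (correct) | In a TV-44749 column (wrong) |
| Worsened on TV-44749, one record | Not in a TV-44749 column (wrong) | In a TV-44749 column (correct) |

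Each reading gets one row wrong, and nothing in the SAP chooses between them. The Period 1 grade problem in trace A arises under both.

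**Size.** Inputs are about 640 randomized, about 440 completing week 8 (SAP 2.5), and allocation 1:1:1:1 then 1:1:1. I assume equal completion across arms and that every completer enters Period 2. Randomized numbers stand in for treated numbers.

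- Placebo patients: 640 / 4 = 160.
- Completion: 440 / 640 = 68.75%.
- Crossing over: 160 × 0.6875 = 110, or about 37 per dose.
- Pooled integrated TV-44749: 3 × 160 + 110 = 590.

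The documents give no rate for events that span the crossover and worsen. Assume that 5 to 15% of those crossing over have an event ongoing at Visit 11, and that 10 to 25% of those worsen or become serious on TV-44749:

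- Low: 110 × 0.05 × 0.10 = 0.55 patients.
- High: 110 × 0.15 × 0.25 = 4.1 patients.

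Rounded to 1 to 4 patients, that is 1/160 to 4/160, or 0.6 to 2.5 percentage points of the Period 1 placebo column. It is 1/590 to 4/590, or 0.2 to 0.7 points of the pooled integrated column. For other rates, each 1% of crossing patients affected is 1.1 patients, which is 0.7 points and 0.2 points respectively. Using the 675 already randomized at 29 January 2024 (Protocol Amendment Details) gives 675 / 4 × 0.6875 = 116 crossing over, which changes little.

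**The case against.** The strongest case on the other side is that the 8.4 sentence is a guard against counting one spanning event twice and does not mention worsening. Several parts of that case stand.

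- **Loss from the drug tables is not certain.** Taken literally with SAP 3.3, the second half of the 8.4 sentence puts the event in the TV-44749 column, which counts against the drug. What the text establishes is a conflict with SAP 8.1.
- **The carry-back is not specific to placebo.** A patient on active drug whose Period 1 event worsens in Period 2 is also reported in Period 1 at the later grade. All four Period 1 columns can be affected, three of them active. Only former-placebo patients are misattributed between placebo and drug.
- **A site may open a new record.** Protocol 8.1.1 allows a worsening to be its own event, and after a gap it is attributed correctly. The CRF completion rules are not in the documents.
- **The worst cases stay visible.** Serious events, deaths, and events leading to discontinuation or withdrawal are listed by patient (SAP 8.4), and deaths have their own table (SAP 8.5). IDMC closed reviews separate patients who roll over from placebo (SAP 8.1).

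These points limit the concern without removing it. The listings show the dose at onset, which for these events is placebo, and SAP 8.4 names no patient listing for severe events that are neither serious nor treatment-ending. An outcome that depends on site recording practice and on an unstated order of rules needs to be specified. The protocol's own integrated analysis (Protocol 10.7) counts these patients as placebo in Period 1 and at their actual dose afterwards. SAP 17 lists no change that would explain the difference.

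**Conclusion.** The point holds as a fault of specification. When followed, the SAP's rules can show an event that worsened on TV-44749 in the Period 1 placebo column at its on-drug grade. For the integrated tables they give two incompatible instructions, each of which is wrong for one kind of former-placebo event.

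A reader might go further and infer that harm on drug is always charged to placebo and lost from the drug tables, so that the SAP errs in the drug's favour twice. The documents do not support that. The 8.4 clause may keep the event in the drug column, the carry-back can also raise the three active columns in Period 1, and separately recorded worsening after a gap is placed correctly. A net bias towards TV-44749 would also need more worsening in newly exposed patients than in continuing ones, and the documents give no information on that.

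The size is likely a few patients: about 1 to 4 of roughly 110 crossing over. This rests on rates that I assumed, and on every completer entering Period 2, although entry also requires clinical stability. No hypothesis test is shown to change. The change is still worth making, because severe and serious counts are low and the correction is cheap.

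**What to change.** Amend the SAP as follows.

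1. Reconcile 8.1 with 8.4, so that one rule governs placebo-onset events in the integrated tables. Word it to cover events with no end date as well.
2. In Period 1 tables, for all four arms, use the worst severity and seriousness reached before the Visit 11 injection.
3. In the integrated tables, define treatment-emergent relative to the first TV-44749 injection: new onset after it, or an increase in severity or seriousness after it. Attribute such events under the existing column rule in SAP 3.3 (initial TV-44749 dose received). Keep unchanged placebo-onset events in Period 1 only.
4. Apply the record-merging rule within a period only.

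The cost is SAP wording, one derivation flag, and a few data queries for the date of worsening where the CRF holds a single record. The downside is possibly a few more events in the TV-44749 columns.

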8.5. Deaths

A summary table and detailed listing will be provided of deaths by treatment group.

8.6. Clinical Laboratory Tests

Clinical laboratory tests (serum chemistry, hematology, urinalysis) are detailed in Table 9 of the study protocol. Central laboratory value and changes from baseline will be summarized.

Laboratory test results will be presented in standard international (SI) units. Listings will include all laboratory values (central and local laboratories).

Laboratory test results will be presented for Period 1 and for the integrated study periods.

Summary statistics for chemistry, hematology and urinalysis laboratory tests will be presented at time points detailed in the Schedule of Assessment Table 1 and Table 2 of the study protocol.

Laboratory values and changes from baseline to each scheduled visit will be summarized using descriptive statistics.

Shifts (below, within, and above the normal range) from baseline to each scheduled visit including "at any visit" assessment (as a separate visit) will be summarized using patient counts. Summaries of potentially clinically significant abnormal values will include all post-baseline values (including scheduled, unscheduled, and withdrawal visits). The incidence of potentially clinically significant abnormal values will be summarized for laboratory variables using descriptive statistics with the criteria specified in [Table 2](#) below.

Summaries will be presented for the While on treatment period (starting from the baseline visit in Period 1 to the EOT visit, including ET visit if conducted during this period). A separate summary will be presented for the Follow-Up period (any visit conducted after EOT visit and until the end of the study).

Table 2: Criteria for Potentially Clinically Significant Laboratory Values

Test	Criterion value
Serum chemistry	
Alanine aminotransferase (ALT)	$\geq 3x$ ULN
Aspartate aminotransferase (AST)	$\geq 3x$ ULN
Alkaline phosphatase	$\geq 3x$ ULN
Lactate dehydrogenase (LDH)	$\geq 3x$ ULN
Blood urea nitrogen (BUN)	≥ 10.71 mmol/L
Creatinine	≥ 177 μ mol/L
Uric acid	≥ 625 μ mol/L
Men	
Women	≥ 506 μ mol/L
Bilirubin (total)	$\geq 2x$ ULN
Potassium	≤ 3 mmol/L ≥ 6 mmol/L
Calcium	≤ 1.5 mmol/L ≥ 3.5 mmol/L
Hematology	
Hemoglobin	≤ 115 g/L
Men	
Women	≤ 95 g/L
White blood cell (WBC) counts	$\leq 3 \times 10^9$ /L $\geq 20 \times 10^9$ /L
Absolute neutrophil counts (ANC)	$\leq 1 \times 10^9$ /L
Platelet counts	$\leq 75 \times 10^9$ /L $\geq 700 \times 10^9$ /L

ULN=upper limit of normal range.

